5.4 Criteria for Initiation of Trial Treatment

When subjects enter this study, they will be randomized to either of the two treatment groups at ratio 1:1 by the randomization schedule generated by a computer program. Considering these two treatments have differences in both administration route and dose, this study is open-label, randomized, controlled clinical study.

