5.1 Overall Trial Design and Plan

This is a multicenter prospective study which will observe the cumulative live birth rates (CLBRs) of gonadotrophin-releasing hormone (GnRH) antagonist protocol compared with the standard GnRH agonist long protocol for controlled ovarian stimulation in supposed normal ovarian responders in China. The recruitment period is planned to start on March, 2018 and to last for 2 years, last-subject-out is expected in December 2020.

This study is planned to involve 5 hospitals and recruit 888 female subjects. Relevant data according to study requirements will be recorded in standard case report form (eCRF). When the study initiates, each reproductive center will screen and enroll qualified subjects to enter the treatment. If a subject has entered the study and later discontinues from the treatment cycle, the reason of discontinuing the treatment should be recorded in eCRF.

Each subject will be followed up to 2 years until she has one live birth or all her embryos are used up after one initiated COS, including fresh & frozen-thawed embryo transfers. Subjects who do not obtain live birth but with embryos left for FET in the 2 years follow up will not be analyzed as drop-out cases either and the CLBR for those patients will be calculated and analyzed in appropriate statistical methods.

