6.10 Blinding

Not applicable.

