7.2.5 Embryo Transfer in fresh cycle

IVF/ICSI, ET and luteal phase support will be performed according to the site's routine practice. Luteal phase support will be started after oocytes retrieval.

The following data will be collected:

- Date of oocyte insemination
- Number of oocytes inseminated
- Endometrial assessment
- Embryo quality
- Methods of insemination
- Number of oocytes fertilized

- Total number of good quality embryos
- Total number of embryos
- Date of embryo transfer
- No. of embryos transferred
- No. of embryos cryopreserved
- Recording of AEs
- Concomitant medications prescribed and reasons.

If the procedure of insemination is not conducted due to any reason, reasons should be specified and all procedures related to End of Study Visit should be performed.

If the procedure of ET in fresh cycle is not conducted and there are no embryos preserved for frozen embryo transfer (FET), reasons should be specified and all procedures related to End of Study Visit should be performed.

If the procedure of ET in fresh cycle is not conducted but there are embryos preserved for FET, further FET visit should be performed.

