8.1 Sample Size

For this non-inferiority trial, a sufficient number of subjects will be enrolled to have at least 80% power to demonstrate the non-inferiority of GnRH antagonist protocol vs GnRH agonist protocol regarding the CLBR using a two-sided 95% confidence interval. The CLBR is expected to be 60% in both groups, and the non-inferiority margin is -10% (absolute). Based on these assumptions, a

sample size of 377 evaluable subjects per arm would provide 80% power to demonstrate the non-inferiority of GnRH antagonist protocol vs GnRH agonist protocol regarding the CLBR. As a result, totally about 888 subjects will be randomized, that is 444 for each treatment group after considering 15% dropout rate.

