8.3.2 Secondary Endpoints

COS and pregnant outcomes, including:

- Number of oocytes retrieved
- Good-quality embryo rate(The Istanbul Consensus1)
- hCG positive rate (in fresh cycle)
- Implantation rate (in fresh cycle)
- Clinical pregnancy rate (in fresh cycle)
- Ongoing pregnancy rate(in fresh cycle)
- Live birth rate(in fresh cycle)
- Cumulative clinical pregnancy rate
- Miscarriage rate(in fresh cycle)
- Ectopic pregnancy rate(in fresh cycle)
- Cycle cancelled rate and reason(in fresh cycle)
- Rate and severity of OHSS(in fresh cycle)
- Time to pregnancy
- Time to live birth

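### The reason given for open label does not cover the laboratory: those who grade embryos for the good-quality embryo rate could be masked to arm

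*Combined protocol and SAP*

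**What the plan says.** Section 5.4 of the combined protocol and SAP gives the whole justification for open label: "Considering these two treatments have differences in both administration route and dose, this study is open-label, randomized, controlled clinical study". Section 6.10 (Blinding) reads, in full, "Not applicable", and 6.11 (Emergency Unblinding) says the same. No section masks an embryologist, a sonographer or any other assessor.

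Good-quality embryo rate is a secondary endpoint in 7.3.2, 8.3.2 and 8.5.3, with the Istanbul Consensus cited as the grading standard. Section 7.2.5 collects embryo quality, "Total number of good quality embryos" and "No. of embryos cryopreserved". On procedure it says only that "IVF/ICSI, ET and luteal phase support will be performed according to the site's routine practice".

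Under 5.1, each woman is followed for up to two years, until a live birth or until "all her embryos are used up after one initiated COS, including fresh & frozen-thawed embryo transfers". Sections 7.2.5, 7.2.7 and 7.2.8 send a woman without a pregnancy on to a frozen transfer only if embryos remain. Otherwise she goes to the End of Study visit.

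**The concern.** A reason that fits two roles has been applied to all of them. The woman injects the drugs and the clinician prescribes them, so neither can sensibly be masked. Grading starts after stimulation is over, and nothing in the documents says that the grader needs to know which GnRH analogue was used.

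Grading involves judgement even under a published standard. A grader who knows the arm and has a view on the two protocols may shift borderline calls. Such views are likely: Sections 3 and 5.2 describe a continuing debate with conflicting evidence. Any arm-related shift goes straight into the good-quality embryo rate. If the same judgement also influences which embryos are kept or transferred, it could reach CLBR indirectly.

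**Working it through.** **Does the stated reason reach each role?**

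- Woman: takes the drugs, so a difference in route and dose reveals the arm. The reason applies.
- Treating clinician: prescribes, monitors and adjusts. The reason applies.
- Embryo grader: works on oocytes and embryos after retrieval. Neither route nor dose is visible in the material. The reason does not apply, and 5.4 and 6.10 give no other. The documents do not name who grades; I take it to be laboratory staff.

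**Does allocation knowledge reach an endpoint?**

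- Good-quality embryo rate: yes, directly, because the grade is the endpoint. The documents give no expected value for this rate and no grading agreement, so the bias cannot be sized.
- CLBR: only through a further step. Frozen transfers count toward it (5.1), and a woman without preserved embryos has no further chance. But 7.2.5 records the number frozen as a data item only. No section ties freezing, discarding or order of transfer to grade, or says who decides.

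**Sample size, reproduced.** Inputs from 8.1: CLBR 60% in both arms, margin 10 points, two-sided 95% interval (one-sided 0.025), power 80%, dropout 15%.

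- n per arm = (1.960 + 0.842)² × (0.6×0.4 + 0.6×0.4) / 0.10² = 7.849 × 0.48 / 0.01 = 376.7, rounded up to 377.
- 377 / (1 − 0.15) = 443.5, rounded up to 444 per arm; 2 × 444 = 888.

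Both agree with the plan. Masking graders changes none of these inputs, so the numbers stand.

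**Sensitivity of the non-inferiority test, illustration only.** The bias b is assumed; nothing in the documents supports a particular value. At 377 per arm:

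- Type I error at the margin (60% against 50%) with a bias favouring the antagonist = Φ(b/SE − 1.960), where SE = √[(0.24 + p(1−p))/377] and p = 0.50 + b. For b = 0.01, SE = √(0.4899/377) = 0.0360, giving Φ(−1.683) = 4.6%.
- Power at true equality with a bias against the antagonist = Φ((0.10 − b)/SE − 1.960), with p = 0.60 − b in the same SE.

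| Assumed bias in CLBR (points) | One-sided type I error | Power |
|---|---|---|
| 0 | 2.5% | 80.0% |
| 0.5 | 3.4% | 75.8% |
| 1 | 4.6% | 71.1% |
| 2 | 8.0% | 60.8% |
| 3 | 13.0% | 49.7% |

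The table shows what a bias of each size would do. It does not show that any such bias exists.

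**The case against.** The case for leaving the plan alone has substance. Live birth is objective. Good-quality embryo rate is one of 14 secondary endpoints, which 8.5.3 describes as supplementary, and it is tied to an external grading standard. Masking would be imperfect: Section 3 expects fewer oocytes with the antagonist, and 7.2.3 mentions a GnRH-a trigger on the antagonist side, so yield or trigger details could hint at the arm. Clinicians would stay unblinded, and cancellations for OHSS risk or by investigator or subject decision (7.2.11) would remain open to influence. All of this limits the importance of the point. None of it explains why graders should know the arm, and partial masking still reduces bias in a judged endpoint.

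Four stronger readings are tempting, and the documents do not support them.

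- *Freezing depends on the grade, so CLBR is biased.* This is a reasonable inference about laboratory practice, but no freezing rule is written.
- *The CLBR bias is a sizeable share of the margin.* One could suppose that 2% to 5% of women gain or lose a last transferable embryo carrying a 30% to 50% chance of live birth: 0.02 × 0.30 = 0.6 points, 0.05 × 0.50 = 2.5 points. With a 5% to 20% chance instead, the result is 0.02 × 0.05 = 0.1 to 0.05 × 0.20 = 1.0 points. None of these inputs has a source, so the answer simply follows the choice. The 50% value is also hard to accept for a borderline embryo when the plan expects 60% from all transfers together.
- *The bias could not be detected.* Sections 7.2.4 and 7.2.5 collect oocytes, MII oocytes, fertilized oocytes, total and good-quality embryos, and embryos transferred and frozen. Good-quality or frozen embryos per fertilized oocyte can be compared by arm. That would not fully separate bias from a treatment effect, but it is not blind to it.
- *Masking would cost almost nothing.* The documents do not describe laboratory records or workflow at the sites, so this cannot be shown from them.

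**Conclusion.** The plan gives no reason for leaving embryo graders unmasked. The established exposure is assessment bias in the good-quality embryo rate, of unknown size and direction. An effect on CLBR is possible but indirect, rests on an unstated link between grading and what is kept or transferred, and cannot be sized from the documents. The conclusion assumes that laboratory staff do the grading and have no need to know the arm; the documents contradict neither. The sample size is unaffected. This is a minor design improvement worth making, not a defect that undermines the non-inferiority test.

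**What to change.** In 5.4 and 6.10:

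- limit the open-label statement to women and treating clinicians;
- state that the existing embryologists who grade and select embryos are masked to arm;
- keep arm, stimulation protocol and trigger type off laboratory request forms and dish labels where feasible, using the subject number instead.

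In 7.2.5, add an eCRF item recording whether the grader knew the arm.

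The cost is a few lines of protocol text, revised laboratory forms and labels, and one eCRF item. No extra reader, visit or participant is needed, and the target stays at 377 evaluable and 444 randomized per arm (888 in total). The drawback is incomplete masking where oocyte yield or site records hint at the arm; the eCRF item shows how often the grader knew.

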5.5 Criteria for Subject Withdrawal

5.5.1 Withdrawal from Trial Therapy

A subject must be withdrawn from trial therapy if any of the following occur:

- Subject withdrew consent
- Subject lost to follow up
- Participation in another clinical trial
- Any events that unacceptably endanger the safety of the subject.

5.5.2 Withdrawal from the Trial

Subjects may withdraw from the trial at any time without giving a reason. Withdrawal of consent will be considered withdrawal from the trial.

A subject must be withdrawn if any of the following occur during the trial

- Subject withdrew consent
- Participation in another clinical trial

5.6 Premature Termination of the Trial

At any time of the study, due to adverse events, investigators determine risks outweigh the benefits. The Sponsor may discontinue the trial if it becomes unjustifiable for medical or ethical reasons, for poor enrollment, or because of comparator from the market for safety reasons. Patients need to receive treatment of forbidden combined medications.

Health Authorities and Independent Ethics Committees (IECs) will be informed about the discontinuation of the trial in accordance with applicable regulations.

5.7 Definition of End of Trial

Subjects who meet primary endpoints or complete 2 years follow-up can complete the study. Primary endpoint is cumulative live birth rates with first live birth resulting from one initiated COS cycle.

A clinical trial may not be considered closed as long as:

- Visits specified by the protocol are still taking place,
- Procedures or interventions according to the protocol are still being undertaken in any subject,
- The post-treatment follow up period, defined in the clinical trial protocol as being part of the trial, has not yet been completed for any subject.

6 Investigational Medicinal Product and Other Drugs Used in the Trial

6.1 Description of the Investigational Medicinal Product

This trial aims to compare GnRH antagonist or agonist **protocols** (described in section 6.2) for COS in ART treatment, not focusing on compare the efficacy and safety for **drugs** used in these two protocols. Drugs used in this study are introduced as followed.

NOTE: All the following introductions are excerpted from the full prescribing information. Dose adjustments can be performed depends on the clinical practice and the special details of each patient.

Cetrorelix acetate for injection (Cetrotide[®]) is a gonadotropin-releasing hormone (GnRH) antagonist used to prevent premature ovulation in controlled ovarian stimulation prior to assisted reproductive technologies (ART). Treatment with Cetrotide[®] should be carried out by a doctor who has experience in this type of fertility treatment. Cetrotide[®] is given by injection under the skin of the lower abdomen (belly). The recommended dose is 0.25 mg given every 24 hours, either in the morning or in the evening. Treatment starts on day 5 or 6 of ovarian stimulation, and is continued throughout the ovarian stimulation period, until the evening before or the morning of the day when the induction of ovulation (the release of eggs) is planned. Because of the risk of severe allergic reactions, the first injection should be supervised by a doctor, and the patient closely watched for 30 minutes. Further injections may be given by the patient herself, as long as she is made aware of the signs of allergic reaction and what to do if they appear. The medicine should be injected slowly at different places on the abdomen every day.

Triptorelin embonate (Diphereline[®] or Decapeptyl[®]) belongs to a group of medicines called Gonadotrophin Releasing Hormone analogues (GnRHa), often be used in ART in combination with gonadotrophins for COS in vitro fertilization and embryo transfer (IVF-ET). GnRH-a should be administered for about 14 to 20 days for down-regulation.

Follitropin alfa (Gonal-f[®]): As a r-FSH agent, Gonal-f[®] is used for COS. It is a prefilled ready to use pen device containing follitropin alfa for injection and is designed for subcutaneous self-

administration by patients undergoing COS for ART. It is available as dose presentations of 300 IU and 450 IU. The investigators and/or his/her delegate/s will explain the use of new Gonal-f[®] prefilled pen, the dose and route of administration (subcutaneous) to the patients to administer the injections at home. Trainings will be provided to study nurses about how to use Gonal-f[®] new pen. Study nurse in turn will provide training to patients on how to self-inject the new Gonal-f[®] pen subcutaneously. The 75IU Gonal-f[®] can also be used as required. If in the course of treatment, in the clinical judgment of the investigator, once the patient meets the criteria of suboptimal ovarian response, the patient needs to receive luteinizing hormone (LH) supplementation, this is permitted as long as no urinary products are used as stated in the exclusion criteria. The daily dose of LH data will be captured in the eCRF.

Lutropin alfa (Luveris[®]) is a luteinizing hormone (recombinant human LH) for the treatment of female infertility. The physicochemical, immunological, and biological activities of Luveris[®] are comparable to those of human pituitary LH. In the ovaries, during the follicular phase, LH stimulates theca cells to secrete androgens, which will be used as the substrate by granulosa cell aromatase enzyme to produce estradiol, supporting Follicle-Stimulating Hormone (FSH)-induced follicular development. Luveris[®] is administered concomitantly with Gonal-f[®] (follitropin alfa for injection) to stimulate development of a potentially competent follicle and to indirectly prepare the reproductive tract for implantation and pregnancy.

6.2 Dosage and Administration

GnRH-a group: GnRH-a types, GnRH-a and FSH doses will be adjusted according to the clinical experiences of investigators in each site. GnRH-a (Diphereline[®] or Decapetyl[®]) 0.1mg administered for about 14 to 20 days for down-regulation is recommended if applicable. Gonal-f[®] will be administered as routinely practiced by investigators. (Daily dose should follow China PI)

GnRH-ant group: The GnRH-ant (Cetrotide[®]) will be initiated in a fixed protocol on stimulation days 5 or 6 per the investigator's ART protocol. Recombinant FSH (Gonal-f[®]) will be administered as routinely practiced by investigators. FSH doses will be adjusted according to the clinical experiences of investigators.

LH supplementation: If there is slow/suboptimal response in follicular development observed by investigators, the rLH (Luveris[®]) will be administered as required. LH supplementation is based on one of the following criteria:

- Having no follicle >10 mm by day 6;
- Low estradiol concentration <200 pg/ml or <732 pmol/L by day 6;
- Poor progression or slowing of follicle growth, i.e., previously 1–2 mm progression/day slowing to less than 2 mm in 3 days.

6.3 Assignment to Treatment Groups

An Interactive Web Response System will be used in this study for the randomization procedure. Subjects will be randomized and assigned to GnRH-a group or GnRH-ant group. Statistical aspects of randomization, including stratification, will be described in Section 8.2.

6.4 Non-investigational Medicinal Products to be Used

Not applicable

6.5 Concomitant Medications and Therapies

Concomitant medications related with COS taken by the subject during the trial, from the date of signature of informed consent are to be recorded in the appropriate section of the eCRF, noting the name, dose, duration and indication of each drug. Nondrug interventions and any changes to a concomitant medication or other intervention related with COS should also be recorded in the eCRF.

6.5.1 Permitted Medicines

Any medications that are considered necessary to protect subject welfare and will not interfere with the trial medication may be given at investigator's discretion.

6.5.2 Prohibited Medicines

Drugs will interfere with the trial medication and other ART treatment drugs (for example uFSH, hMG, etc.).

6.5.3 Other Interventions

Not applicable

6.5.4 Special Precautions

Cetrotide[®], Diphereline[®], Decapetyl[®] and Gonal-f[®] are all prescribed by the physicians and bought by patients themselves.

Luveris[®] will be provided for free once patients meet at least one of following criteria

- Having no follicle >10 mm by day 6;
- Low estradiol concentration <200 pg/ml or <732 pmol/L by day 6;
- Poor progression or slowing of follicle growth, i.e., previously 1–2 mm progression/day slowing to less than 2 mm in 3 days.

6.5.5 Management of Specific Adverse Events or Adverse Drug Reactions

Not applicable

6.6 Packaging and Labeling of the Investigational Medicinal Product

All IMPs will be packaged and labeled in commercial packaging.

6.7 Preparation, Handling, and Storage of the Investigational Medicinal Product

Drug preparation

Investigational drug:

All investigational drugs are prescribed for subjects in clinic by investigators. The study site does not provide Cetrotide[®], Diphereline[®], Decapetyl[®] and Gonal-f[®] for free, but in some specific situation Luveris[®] will be provided for free, which was listed in section 6.5.4.

Drug storage

Drugs will be stored in clinical study sites. Drugs are prescribed by investigators and subjects get them in the pharmacy, see Section 6.5.4.

6.8 Investigational Medicinal Product Accountability

All drugs involved in the study are prescribed to subjects by investigators and subjects go to the pharmacy of clinic and buy drugs according to the prescription.

6.9 Assessment of Investigational Medicinal Product Compliance

Investigators check investigational drug usage of subjects regularly and record it in original medical record.

6.10 Blinding

Not applicable.

6.11 Emergency Unblinding

Not applicable.

6.12 Treatment of Overdose

An overdose is defined as any dose greater than the highest daily dose included in a clinical trial protocol or planned for an individual subject enrolled in the trial, even if it does not meet other criteria for an SAE. If investigational drug is overdose, the subject will be judged by investigators and determined whether to continue in the study or not. And usage, dose and date of overdose will be recorded in original medical record. Any overdose must be recorded in the trial medication section of the eCRF and reported to Drug Safety in an expedited manner using the SAE Report Form, and following the procedure in Section 7.4.

6.13 Medical Care of Subjects after End of Trial

Conduct according to clinical practice.

7 Trial Procedures and Assessments

7.1 Schedule of Assessments

All subjects' data will be collected in anonymity. The subjects are assigned to the two treatment groups at the ratio 1:1 using blocked randomization method according to a randomization schedule generated by the statistician using a computer program. Each subject will have a unique subject number assigned to her and this will be referenced throughout the study as the subject's identifier. The Investigator should keep a separate code identification list with subjects' information to be retained at the site.

After randomization, the subjects will receive either GnRH-a long protocol or GnRH- ant protocol for COS in supposed normal ovarian responders.

The data collection time points for two protocols are as follows:

Screening/Baseline

Gonadotrophin (Gn) Initiation

Triggering Day

Oocytes Pick up

Embryo Transfer

HCG test: Serum β -hCG test after 11 to 17 days of ET

Clinical Pregnancy Assessment: Ultrasound examination after 4 to 6 weeks of ET

Ongoing Pregnancy Assessment (fresh cycle)

Live Birth Assessment

FET cycles

Follow up Visit

In each frozen embryo transfer (FET) cycle, the data regarding hCG results, clinical pregnancy and live birth will be assessed and collected.

